13.5 Health Care Utilization Data Analysis Plan

Overview of analysis

The health care utilization analysis is designed to explore the effects of the intervention on the use of health care services by the study participant, specifically primary care visits, emergency room/department visits and inpatient utilization. The pilot project that preceded the development of this randomized controlled trial did not collect health care utilization data; therefore, this aspect of the analysis will provide new information on whether the intervention affects health care utilization. There is an opportunity to collect both self-reported health care utilization data from study participants before (T0) and at the conclusion of the six-month intervention or waitlist period (T6), as well as six months following completion of the intervention or waitlist period (T12). A survey will also be sent to primary care providers for records of selected services for both the intervention and waitlist groups after the initial six month enrollment period (T6). This survey will request data for the six month period prior to enrollment, as well as the six months the study participant was enrolled in either the intervention or waitlist group. At T12, the same survey will be sent to providers caring for original intervention study participants and will request data for the period between T6 and T12. Providers caring for individuals in the original waitlist group will not be surveyed at T12.

The participant and provider data can provide insight on whether the intervention has an effect on the utilization of selected health care services, and by using geographically adjusted cost averages for the associated services, can provide some general information on potential cost implications for those utilization patterns. Other data that can inform the analysis, such as participant self-reported health status, health care coverage status and reports of missed time at school or work will also be included in the analysis.

13.5.1 Participant and provider data collection process

Self-reported data on the use of selected health care services will be collected from all participants in the survey administered at enrollment (T0), after six months in the study (T6), and again six months after completion of the initial intervention or waitlist period (T12) (see **section 7.6** for a general description). In each survey, the study participant will be asked to report on health care utilization in the prior six months. At enrollment (T0), the participant will also be asked to provide consent for the release of medical record information from their current primary care provider during the enrollment process.

If the participant reports he or she does not currently have a primary care provider, the participant will be given an active referral if part of the treatment group and offered a provider resource sheet if part of the waitlist control group.

After the participant has been in the study for six months, the site RA will send a health care utilization survey to the primary care provider the participant identifies at enrollment. The site RA will also ask if there has been any change in primary care provider during the prior six months and will send additional surveys as appropriate. The provider survey will be accompanied by (see **Appendix Y**) a brief explanation of the survey and contact information for any questions or assistance needed in completing the request, as well as a copy of the signed HIPAA and medical records release authorization.

The T6 provider survey will query dates of service for primary care visits made in the past 12 months for each participant (the six month period prior to enrollment, and the following six month period during the intervention or waitlist window), as well as the primary associated CPT codes and up to four ICD-9/ICD-10 diagnosis codes. The provider survey is not restricted to services provided for diabetes or diabetes complications since it may be difficult to discern whether a particular condition is associated with or affected by diabetes. The provider survey will also ask for dates of any scheduled but missed appointments. Providers will be asked to list the dates of service, primary procedure codes and diagnosis codes for any emergency department visits or inpatient hospital admissions for which they have records. Although the records of these services may be less complete than those delivered directly by the provider practice/clinic, it is standard practice for hospitals to forward discharge summaries if a provider is identified at the time of admission and we will obtain this information whenever possible.

At T12, provider surveys will be sent only to those providers who have cared for a study participant originally enrolled in the intervention group. The information collected will be identical to that requested at T6, but will focus on utilization during the intervening six-month period. Providers who cared for a study participant originally enrolled in the waitlist group will not receive a survey for that participant.

See **section 7.7** for additional details on the processes for communicating with providers and obtaining completed health care utilization surveys.

13.5.2 Health care utilization indicators and hypotheses

One of the four arms of the intervention is the active referral to a primary care provider if the participant does not have one at the time of enrollment. In addition, the self-management support (SMS) activities in the intervention are designed to reinforce engagement of the participant with the primary care provider as a component of their diabetes management. Thus, our primary indicator will be change in the reported utilization of primary care services, as assessed by self-reported data and provider reports where available.

Our hypothesis is that the intervention participants will have increased engagement with their primary care provider when compared to the control group, and when compared to their level of engagement prior to the intervention. Because this particular model is unique in its use of food pantries as a point of outreach and support and its incorporation of a diabetes-focused food security intervention, there is no prior literature that directly informs our hypothesis development. However, we can draw some insight for hypothesis development from other studies of the impact of self-management support models on health care utilization. For example, Hamid et al. (2014) reported on a cluster-randomized design used to assign 268 diabetes patients to a nurse-community health worker intervention or usual care. Hospitalizations, emergency department, and primary care physician visits were collected retrospectively for one year prior to, and during, the intervention to assess changes in health care utilization. Adjusted incidence rate ratios for primary care physician visits were significantly higher in the community health worker intervention relative to the usual care. The authors found no main intervention effect on emergency department utilization, but visits in the prior year modified the intervention effect on emergency department visits. Increased primary care physician utilization was associated with greater decreases in HbA1c.

In a review of studies implementing at least some features of chronic disease management models (including SMS), Bodenheimer, Wagner and Grumbach (2002) reported mixed evidence on the impact of diabetes interventions on health care utilization. However, the authors were surprised to note that while they expected shorter-term interventions would not affect diabetes health care utilization or costs because of the relatively long horizon for the evolution of disease complications, some studies suggested that even shorter-term interventions reduced utilization in some services, including the length of hospital stays, fewer hospital stays and reduced utilization of emergency department visits. Some studies failed to show a reduction in overall health care costs; at least one did show a reduction in emergency department and specialty visits but not overall costs.

It is not clear whether this intervention can be expected to have a significant impact on reducing the use of more intensive services, especially since neither diversion of patients from more intensive services nor intensive chronic disease management are specific aims of the study, and there is no change in payment incentives related to utilization. However, based on some evidence of reduced utilization associated with SMS and community-oriented models in the literature, our secondary indicators will include changes in inpatient hospital stays, inpatient hospital length and number of emergency department visits. We hypothesize that there may be some trend toward reduction in more intensive services, at least for those with sufficient uptake of the intervention.

In some cases, however, it is possible that increased utilization might be observed and even desirable; for example, if patients learn to identify high-risk health situations more effectively and seek treatment as a result of the intervention. An analysis of primary diagnostic codes associated with utilization will be conducted to assess the extent to which utilization appears to be associated with diabetes-related conditions, especially more acute events such as severe hypoglycemia. We will also examine whether there is an association between changes in health care utilization and improvement in the primary study indicator of improved HbA1c.

13.5.3 Sample size estimation

The health care utilization analysis will utilize the sample generated by the FAITH-DM study. The estimated recruitment goal for the project is 720, with a projected sample size of 600 (300 each in intervention and waitlist arms) after estimated loss to follow-up of 20%. This sample provides the basis for the analysis of the self-reported utilization data and the pool of participants from which provider surveys will be requested. It is our goal to collect provider data from at least 80% of the intervention participants and 70% of the waitlist control participants (it is anticipated that this group will yield fewer primary care provider relationships, since they are not receiving the intervention that supports these). The pilot project upon which this study was based suggested that most individuals who participated in food pantry screening reported that they had a primary care provider at the time of their enrollment in the pilot project. However, prior health records were not requested from those providers in the pilot so it is difficult to know prospectively how many provider contacts will actually yield records, given that individuals struggling with food insecurity may also have been disconnected from health care access in the months prior to their recruitment at the food pantry.

13.5.4 Statistical analyses

For each of the outcomes from the utilization analysis we would assess the impact of the intervention using the following specification:

$$Y_i = \beta_0 + \beta_{1,i}T + \beta_{2,i}Post + \beta_{3,i}T * Post + \epsilon_i$$

Where Y_i is the given outcome variable, T_i is an indicator for being assigned to treatment, $Post$ is an indicator that the observation is from the post intervention time period, and ϵ_i is the error term. The impact of the intervention is measured by β_3 which measures the intent to treat effect – or the change in the outcome of interest for the treatment group compared to the change in the outcome of interest for the wait-list group. Since randomization is at the individual-level, HuberWhite standard errors will be used.

Loss to follow-up

We intend to follow the same procedures for loss to follow-up as specified in the analysis of the primary study outcome (HbA1c). We will conduct a formal missingness investigation to determine if the attrition rate differed between intervention and waitlist groups. If treatment status is found not to significantly affect attrition at the 5 percent significance level, then all estimation will proceed without

any adjustment for attrition. If attrition is found to be related to treatment status, we postulate that attrition will be higher for the control group, and will employ Lee bounds to obtain bounds on our treatment estimates which are robust to this attrition. Multiple imputation for missing outcome data will also be explored as sensitivity analyses.

Subgroup analyses

While the study is randomizing within sites, we also plan to conduct subgroup sensitivity analyses by both adjusting for site and examining changes within site to determine differential effectiveness by location. Site-specific differences will be shared with the food pantries, but only reported publicly in manuscripts if found to be significantly different.

Other planned subgroup analyses (as specified in our hypotheses) are by baseline glycemic control (>9%) and food security status.

14 Quality Control Procedures

Data integrity and study credibility depend on factors such as:

- Ensuring adherence to the protocol
- Obtaining complete follow-up information on all participants enrolled
- Using quality control measures to establish and maintain high standards for data quality

Quality control procedures for point-of-care testing is described in **section 7**.

Data entry directly into CASIC or MS Access allows for immediate range checks. Data questions will be posed by the study statistician ([name]) to sites as needed. Data quality will be reviewed by the study statistician at least every six months.

Site visits will be conducted annually (or as needed). Protocol deviations will be reviewed within 48 hours to determine if corrective actions need to be taken. This procedure is not intended to be punitive, but to assist with avoiding similar problems across sites in the future.

Ongoing quality control and iterative improvement helps to ensure the highest quality study possible.

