13.4 Data Analysis Plan

13.4.1 Sample size estimation

We used the sampsi program in Stata to calculate the necessary sample size to detect a 0.4% decrease in HbA1c with 90% power. Using our preliminary data from the pilot phase of this project, we projected that the average A1c would decrease from 9.5% to 9.1% with a correlation between the

2 observations per individual at 0.51. Given these parameters, we determined that 300 individuals were needed in both the intervention and waitlist arms of this RCT. In order to allow for 20% attrition from baseline to follow-up, we increased the final recruitment goal to 720 individuals total (240 per site).

sampsi 9.5 9.1, sd1(1.6) sd2(1.9) method(ancova) pre(1) post(1) r1(.51) power(0.9)

Estimated sample size for two samples with repeated measures

Assumptions:

alpha =	0.0500	(two-sided)
power =	0.9000	
m1 =	9.5	
m2 =	9.1	
sd1 =	1.6	
sd2 =	1.9	
n2/n1 =	1.00	
number of follow-up measurements =	1	
number of baseline measurements =	1	
correlation between baseline & follow-up =	0.510	

Method: ANCOVA

relative efficiency =	1.352
adjustment to sd =	0.860
adjusted sd1 =	1.376
adjusted sd2 =	1.634

Estimated required sample sizes:

n1 =	300
n2 =	300

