13.4.3 Hypotheses

We are testing several hypotheses in this study.

1. The primary hypotheses which we are powered to examine is a significant improvement in HbA1c over a 6-month timeframe.
 - a. For all of these outcomes, we also hypothesize that the effect sizes will be largest among those who completed a minimum amount of exposure to all intervention components. A priori, we defined engagement in the intervention components as: picking up 80% of diabetes-appropriate food boxes, attending the 2 required diabetes education classes, and having at least 1 primary care visit over the 6-month follow-up period.
 - b. We also hypothesized that the intervention would have the largest effect on those in the poorest A1c control (>9%) and those with very low food security status at baseline.
2. Secondary hypotheses: The secondary outcomes of interest are improvements in fruit/vegetable intake, diabetes distress, self-reports of severe hypoglycemic events, depressive symptoms, medication adherence, tradeoffs between affording food vs medication/supplies, food security status, and food stability.
3. Healthcare utilization hypotheses/analyses will be covered in a separate analysis plan

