13.4.4 Statistical analyses

For all the outcomes specified above, we will determine significant improvements using an ANCOVA specification:

$$Y_{i,t=1} = \beta_0 + \beta_1 T_i + \pi Y_{i,t=0} + \varepsilon_i$$

Where $Y_{i,t=1}$ is the given outcome variable measured post-treatment, $Y_{i,t=0}$ is its baseline value, T_i is an indicator for being assigned to treatment, and ε is the error term. Since randomization is at the individual-level, HuberWhite standard errors will be used. β_1 will provide the intent-to-treat effect.

Loss to follow-up

We intend to collect follow-up data on at least 80% of participants. We will conduct a formal missingness investigation to determine if the attrition rate differed between intervention and waitlist groups. If treatment status is found not to significantly affect attrition at the 5 percent significance level, then all estimation will proceed without any adjustment for attrition. If attrition is found to be related to treatment status, we postulate that attrition will be higher for the control group, and will employ Lee bounds to obtain bounds on our treatment estimates which are robust to this attrition (<https://ideas.repec.org/c/boc/bocode/s457477.html>). Multiple imputation for missing outcome data will also be explored as sensitivity analyses (<http://aje.oxfordjournals.org/content/175/3/210.full>).

Per protocol/exposure to treatment

Among those with complete baseline and follow-up A1c ascertainment, we will also examine the influence of the amount of exposure to the program. Specifically, we will determine whether the

participants who met our criteria for being “engaged” in the program (overall and by specific intervention component) had larger effects than those who were less engaged.

In this analysis, because the randomization benefits will be lost, we will adjust for other covariates in our model that we hypothesize to influence A1c and self-management improvements: age, gender, race/ethnicity, educational attainment, language, and site/location.

Subgroup analyses

While we are randomizing within sites, we also plan to conduct subgroup sensitivity analyses by both adjusting for site and examining changes within site to determine differential effectiveness by location. Site-specific differences will be shared with the food banks, but only reported publicly in manuscripts if found to be significantly different.

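### Section 13.5.4 estimates utilization effects by difference-in-differences, where the baseline-adjusted ANCOVA of section 13.4.4 would be at least as precise in large samples; the size of the loss rests on quantities the documents do not give.

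*Combined protocol and SAP*

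**What the plan says.** Section 13.5.4 regresses each utilization outcome on treatment T, a post-period indicator and T*Post. The T*Post coefficient is the intent-to-treat effect, described as "the change in the outcome of interest for the treatment group compared to the change in the outcome of interest for the wait-list group". Huber-White errors are specified because randomization is individual. Clustering on participant is not mentioned, and no reason is given for this choice of estimator.

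For the other outcomes, section 13.4.4 says: "For all the outcomes specified above, we will determine significant improvements using an ANCOVA specification". Its equation contains treatment and the baseline value and has no site term; site adjustment is listed as a sensitivity analysis in both 13.4.4 and 13.5.4. Utilization is set apart in 13.4.3: "Healthcare utilization hypotheses/analyses will be covered in a separate analysis plan".

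The baseline data are planned. Under 13.5.1, participants report use over the preceding six months at T0, T6 and T12, and under section 8 the T0 survey comes before the randomization envelope is opened. Under 13.5, the T6 provider survey covers the six months before enrollment and the six months after it, in both arms.

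Section 13.4.1 sizes the trial on HbA1c by ANCOVA, "to detect a 0.4% decrease in HbA1c with 90% power". Section 13.5.3 takes over that sample of 600, gives no power or precision figure for utilization, and aims for provider data on 80% of the intervention arm and 70% of the control arm. Section 13.5 states that the pilot gathered no utilization data.

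**The concern.** Under randomization, any baseline difference between the arms is due to chance. Difference-in-differences removes it by subtracting the baseline in full, which fixes the baseline slope at 1. ANCOVA estimates the slope and so subtracts only as much as the data support. When the best slope is well below 1, full subtraction adds noise from the pre-period. This is the true variance of the estimator, so correct standard errors do not recover it.

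Precision is what this analysis can least spare. It has no power calculation of its own, provider records are expected to be incomplete, and for emergency and inpatient use section 13.5.2 expects only a possible trend. A less precise estimator makes an inconclusive result more likely.

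**Working it through.** **Inputs from the documents.** Two-sided alpha 0.05, power 90%, HbA1c difference 0.4 (9.5 against 9.1), SDs 1.6 and 1.9, r = 0.51 and 1:1 allocation (13.4.1); utilization sample 300 per arm (13.5.3); provider coverage 80% and 70%, so about 240 and 210 of 300 (13.5.3).

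**Inputs not given, so assumed.** For utilization, the pre/post correlation r and k = SD_pre/SD_post. I vary r from 0.2 to 0.6 and k over 0.8, 1 and 1.25.

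**Step 1: the plan's own figure.** n per arm = (z₀.₉₇₅ + z₀.₉₀)² (1.6² + 1.9²)(1 − r²)/0.4².
- (1.95996 + 1.28155)² = 10.507, and 10.507 × 6.17/0.16 = 405.2 without baseline.
- 405.2 × (1 − 0.51²) = 405.2 × 0.7399 = 299.8, rounded up to 300. The relative efficiency is 1/0.7399 = 1.352. Both match the plan, which states: "we determined that 300 individuals were needed in both the intervention and waitlist arms of this RCT".
- For illustration, a change-score analysis on the same inputs needs 405.2 × 2(1 − 0.51) = 397.1, so 398 per arm, or has 80.4% power at 300.

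**Step 2: variances.** In units of the follow-up variance, and up to a common factor:
- Difference-in-differences: 1 + k² − 2rk
- ANCOVA: 1 − r²
- Gap: k² − 2rk + r² = (k − r)², which is never negative and is zero only when r = k.

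**Step 3: share of the sample lost**, 1 − (1 − r²)/(1 + k² − 2rk). At k = 1 this reduces to (1 − r)/2. Example at k = 0.8, r = 0.2: 1 − 0.96/1.32 = 27.3%.

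| r | k = 0.8 | k = 1 | k = 1.25 |
|---|---|---|---|
| 0.2 | 27.3% | 40% | 53.5% |
| 0.4 | 16.0% | 30% | 46.2% |
| 0.51 (HbA1c, borrowed) | 10.2% | 24.5% | 42.5% |
| 0.6 | 5.9% | 20% | 39.8% |

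At k = 1, difference-in-differences on 600 participants carries the information of ANCOVA on 360, 420, 453 and 480. Confidence intervals are wider by √(2/(1 + r)) − 1, which is 29% at r = 0.2 and 12% at r = 0.6. Outside this range of r, the loss at k = 1 is 50% at r = 0 and 10% at r = 0.8.

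**Step 4: difference detectable with 90% power at k = 1**, in SD units, ANCOVA against difference-in-differences.

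| r | 300/300 | 240/210 (provider records) |
|---|---|---|
| 0.2 | 0.259 vs 0.335 | 0.300 vs 0.387 |
| 0.51 | 0.228 vs 0.262 | 0.263 vs 0.303 |
| 0.6 | 0.212 vs 0.237 | 0.245 vs 0.274 |

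**Step 5: simulation.** With 600 participants, normal outcomes and 1,500 replicates, the ANCOVA/difference-in-differences variance ratio was 0.56, 0.77 and 0.80 at r = 0.2, 0.51 and 0.6; the formula gives 0.60, 0.755 and 0.80. With overdispersed counts (mean 1.5 visits, 4,000 trials) the inverse ratio was 1.68, 1.54 and 1.38 at r = 0.20, 0.31 and 0.44; 2/(1 + r) gives 1.67, 1.53 and 1.39. Rarer events were not simulated.

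**Step 6: standard errors.** At r = 0.51 the stacked model reported a Huber-White error of 0.115 without clustering, against an actual 0.079. Clustering on participant gave 0.081.

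**The case against.** The strongest case against is that the size is unknown and may be small. The documents give no correlation or SD for utilization, and the one correlation they do give, 0.51, is for HbA1c. Some of the text suggests k below 1. Section 13.5.3 says participants may have lost contact with care before recruitment, and 13.5.2 expects primary care use to rise in the intervention arm. A lower pre-period mean count usually goes with a lower pre-period SD. At k = 0.8 the loss falls to between 27.3% and 5.9%, and it vanishes where r = k. This stands as a limit on the size, not on the direction.

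Second, 13.5.2 also hypothesizes that intervention participants will increase engagement relative to their own earlier level. The period terms estimate that; ANCOVA does not. This stands, and it is a reason to keep the planned model in a supporting role. It does not help that model as the between-arm estimate, because regressing change on treatment and baseline gives the same treatment coefficient as regressing follow-up on them.

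Third, ANCOVA needs a baseline for each participant. Under 7.7.3.2, someone without a provider at T0 has the T6 survey sent to a new provider, who may hold no earlier records. This also stands, and calls for a stated rule.

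A reader might also infer that the plan contradicts itself, since 13.4.4 claims all outcomes for ANCOVA. It does not: that sentence refers to the outcomes listed before it, and 13.4.3 sends utilization to its own plan.

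**Conclusion.** The point holds as one of efficiency. With 1:1 randomization and large samples, ANCOVA is never less precise than the planned estimator, whatever r and k are. It uses measurements the trial already intends to collect.

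A reader might infer a fixed loss of a fifth to two fifths of the sample, or that six-month counts are known to correlate weakly. The documents support neither. That range is exactly r = 0.6 down to r = 0.2 with equal SDs, and both conditions are assumptions. Across the k values tried, the loss over the same r runs from 5.9% to 53.5%. Likewise, difference-in-differences is worse than ignoring the baseline only if r is below k/2, which is 0.5 at equal SDs.

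Nor is this bias. Difference-in-differences targets the same intent-to-treat effect, and the HbA1c analysis is untouched. Section 13.5 presents the utilization work as exploratory and makes no power claim that this could overturn.

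**What to change.** In 13.5.4, make the main between-arm estimate a regression of follow-up-period utilization on T and the same measure from the six months before enrollment, with one row per participant and Huber-White errors. This is the 13.4.4 form. Add site, because randomization is within site; say so explicitly, since the 13.4.4 equation has no site term.

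State a rule for missing baseline provider records, either a missing-baseline indicator or mean imputation, so that no randomized participant with follow-up data is dropped. Report missing baselines by arm. These records are requested after randomization and only the intervention arm receives an active referral at enrollment, so missingness could differ by arm. If it does, the T0 self-report, taken before randomization, is the safer covariate.

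Keep the T, Post and T*Post model as a sensitivity analysis and to describe the within-arm change hypothesized in 13.5.2, with errors clustered on participant.

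The cost is a revision of the analysis plan, the missing-baseline rule and a little more analysis work. No new data are needed.

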- **Randomization Plan:** We will use a 6-block randomization scheme to ensure that the rolling enrollment process across multiple food bank sites will distribute participants equally into each study arm over time. This scheme will be generated using the website www.randomization.com for each food bank site separately, which will create a list of the order of randomization by sequential participant ID.
- **Process Responsibilities:** UCSF will be in charge of creating the randomization scheme for each site. This will include generating the randomization list, preparing sealed envelopes by participant ID, and mailing them to each site to open as recruitment progresses. In the event a participant ID is not used (e.g., a client withdraws consent upon learning what group he/she is randomized to), site study staff should note the participant ID number, destroy the number and envelope, and report the event and ID number to UCSF. UCSF staff will determine if any adjustments need to be made to maintain balance between assignments to intervention and control groups, and will instruct study staff accordingly.

Participant Identification Numbers by Study Site	
Site	ID Numbers
Houston	101-399
Detroit	401-699
Oakland	701-999

- **Procedure for Randomizing a Participant:** The research assistant at each food bank will enroll participants into the study. No staff member will know the randomly selected allocation of the participant until the HbA1c screening, informed consent process, and baseline survey is completed. At the conclusion of this baseline visit, the staff member will open the sealed envelope that corresponds to the participant ID number of the enrolled client and determine the arm assignment, either immediate intervention or waitlist intervention.
- **Best Practices for Using Randomization Envelopes:** Study staff that participate in enrollment activities should use the following best practices to ensure consistency in the randomization process, and to foster a satisfactory client experience.
 - Have all of your enrollment materials available when you are meeting with a new participant (e.g., consent forms, education materials, survey materials, and randomization envelopes)
 - It is especially important to have the participant’s randomization envelope at your table (and in plain sight) during the entire enrollment process
 - Have only 1 randomization envelope at the table for each participant

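### The health-care-utilisation model uses each participant's before and after records as separate rows but does not cluster the Huber-White errors by participant; with positive within-person correlation its standard errors are too large

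*Combined protocol and SAP*

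**What the plan says.** Section 13.5.4 models each utilisation outcome on T, Post and T*Post. Post "is an indicator that the observation is from the post intervention time period", so the rows are person-periods. The effect of interest is the coefficient of T*Post (β3), described as "the change in the outcome of interest for the treatment group compared to the change in the outcome of interest for the wait-list group". The variance statement reads "Since randomization is at the individual-level, HuberWhite standard errors will be used".

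The periods come from the same people:

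- On the T6 provider survey, Section 13.5 says "This survey will request data for the six month period prior to enrollment, as well as the six months the study participant was enrolled", and Section 13.5.1 says "The T6 provider survey will query dates of service for primary care visits made in the past 12 months for each participant".
- On self-report at T0, T6 and T12, Section 13.5.1 says "In each survey, the study participant will be asked to report on health care utilization in the prior six months".

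Section 13.5.2 hypothesises greater primary care engagement in the intervention arm "when compared to the control group, and when compared to their level of engagement prior to the intervention". That calls for β3 and also for the within-arm change, β2+β3.

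Neither 13.4 nor 13.5 mentions clustering by participant, a participant effect, a mixed model or a change-score analysis.

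**The concern.** Section 13.4.4 uses the same variance sentence for the HbA1c ANCOVA. That model has one row per person, with baseline as a covariate, so plain Huber-White errors suit it. In 13.5.4 each person has two or more rows. The sentence cannot imply clustering in one section and not in the other, and an analyst following the text would run unclustered robust errors.

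The direction is easy to get wrong. Ignoring correlation makes errors too small for a contrast between people. β3 is a contrast of changes within people, where positive correlation is subtracted, so ignoring it makes the errors too large.

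At stake is the inference on every utilisation outcome, including the main one, primary care visits. Section 13.5.3 has no power calculation for these outcomes. It reuses the HbA1c sample and aims for provider data on only 80% of the intervention arm and 70% of the wait-list arm, so precision is already limited. Section 13.5.4 also makes public reporting of site differences depend on significance.

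**Working it through.** **Inputs.** From 13.4.1: SDs 1.6 and 1.9, difference 0.4, correlation 0.51 (for HbA1c), two-sided alpha 0.05, power 90%. From 13.5.3: 720 recruited, 300 per arm projected. The utilisation correlation rho is not given, and 13.5 says the pilot collected no utilisation data, so a range is used.

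**The plan's own figure.** n per arm = (1.6² + 1.9²)(1 − 0.51²)(1.960 + 1.282)² / 0.4² = 299.8, rounded up to 300. It reproduces. It concerns HbA1c; the utilisation section states no standard error or power of its own.

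**Complete pairs.** With n per arm, SD σ and within-person correlation rho:

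- True Var(β3) = 4σ²(1 − rho)/n
- Unclustered Huber-White estimates 4σ²/n
- Inflation factor k = 1/√(1 − rho)
- True size of a nominal 5% test = 2·P(Z > 1.96k)
- Power of a comparison that has 80% under correct errors = P(Z > 1.96k − 2.80)

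The 80% is a hypothetical benchmark. At n = 300 and rho = 0.51 the unclustered SE is √(4/300) = 0.1155 SD and the correct one is √(4 × 0.49/300) = 0.0808 SD, so k = 1.43.

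| rho | SE too large by | True size | Power (80% if correct) |
|---|---|---|---|
| 0.2 | 1.12 | 2.8% | 73% |
| 0.3 | 1.20 | 1.9% | 68% |
| 0.51 | 1.43 | 0.5% | 50% |
| 0.6 | 1.58 | 0.2% | 38% |

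The within-arm change β2+β3 has the same factor: 2σ²/n is used where 2σ²(1 − rho)/n is true. k does not depend on n.

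**Self-report with 20% loss.** 720/2 = 360 before rows per arm, and 360 × 0.8 = 288 after rows. Per arm, in units of σ², the unclustered variance is 1/360 + 1/288 = 0.00625 and the true variance is 0.00625 − 2·rho/360. At rho = 0.51 the true value is 0.00342, so k = 1.35. For rho 0.2 / 0.3 / 0.51 / 0.6, k = 1.10 / 1.17 / 1.35 / 1.46 and power is 74% / 70% / 56% / 47%.

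**One before and two after periods.** With AR(1) correlation, k = √(1.5/(1.5 − 0.5·rho − rho²)) = 1.05 / 1.09 / 1.23 / 1.34. With equal correlation between all periods, k is again 1/√(1 − rho).

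**Negative correlation.** At rho = −0.1 the SE is too small: k = 0.95, size 6.2%.

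**Simulation** (3,000 trials, 300 per arm, rho 0.2 / 0.3 / 0.51 / 0.6):

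- Normal outcome: mean unclustered SE divided by the empirical SD of β3 was 1.11 / 1.19 / 1.43 / 1.59; null rejection 3.0% / 1.9% / 0.5% / 0.2%.
- Overdispersed visit counts (assumed mean 2 per six months): 1.12 / 1.16 / 1.42 / 1.57; null rejection 3.0% / 2.6% / 0.3% / 0.2%.
- Clustered by participant: ratio 0.97–1.00, null rejection 4.8–6.2%, power 79–82%.

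In a further run of 1,500 trials at rho 0.51, with 20% (intervention) and 30% (wait-list) of after rows missing, the unclustered SE was still 1.31–1.32 times too large. The SE of β1, the baseline arm contrast, was not affected in the normal-outcome runs with complete pairs (0.0816 or 0.0817 SD either way).

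**The case against.** The strongest case is that this is minor, uncertain in size, and partly a matter of wording.

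- **Low stakes.** The error neither biases β3 nor, with two periods and positive rho, creates false positives. Section 13.5 frames the analysis as exploratory, 13.5.2 expects at most a trend in intensive services, and 13.5 sets no significance level for the utilisation outcomes. All true. But the intervals and p-values would still be wrong as reported, in an analysis with little precision to spare.
- **Unknown rho.** The 0.51 belongs to HbA1c, rho may differ between visit types, and the error vanishes as rho approaches 0. This stands, which is why a range is shown. The 50% and 38% power figures are illustrations, not forecasts.
- **Direction.** With two after periods, mean before–after correlation a and after–after correlation c, the true variance is proportional to 1.5 + c/2 − 2a, against 1.5 unclustered. If c > 4a the SE is too small even with all correlations positive; a = 0.1 and c = 0.6 gives a factor of 0.97 and size of about 5.8%. This is correct but narrow and small, and clustering cures it too.
- **Complete pairs are optimistic.** Under 7.7.3.2 and 7.7.3.4 some surveys go to a new provider, who may hold no pre-enrolment records. The complete-pair figures are therefore at the upper end for provider data.
- **Ambiguous wording.** The sentence could be naming the individual as the unit for the robust errors. Its identical use for the one-row ANCOVA makes that reading hard to sustain.

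**Conclusion.** The concern holds. Section 13.5.4 uses repeated rows per participant and specifies a variance estimator that treats them as independent. With complete pairs and rho between 0.2 and 0.6, the standard error of β3 is too large by 12% to 58%; with 20% loss of after records, by 10% to 46%. For two periods with positive rho the error is conservative: wide intervals, tests below nominal size, lost power. These sizes rest on an assumed rho and on equal variances across periods and arms. The omission itself rests on no assumption. It should be fixed, but it is confined to the utilisation analysis and leaves the HbA1c ANCOVA untouched.

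**What to change.** In 13.5.4, replace the last sentence of the model paragraph with:

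*Huber-White standard errors clustered by participant ID will be used, because each participant contributes more than one record.*

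This keeps the model, both contrasts in 13.5.2 and the sample. It is valid for either sign of rho, for incomplete pairs, and whichever follow-up records are coded Post (the plan does not say whether T12 records are). The cost is one phrase of text, with no new data and no design change.

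Optional, minor and separate: allocation lists are generated "for each food bank site separately, which will create a list of the order of randomization by sequential participant ID" (Section 8), so site indicators could go in the main models, with the unadjusted models as sensitivity runs. The residual HbA1c variance from 13.4.1 is (1.6² + 1.9²)/2 × (1 − 0.51²) = 2.28. If sites differ by an SD of 0.2 to 0.5 points (assumption), the HbA1c SE would improve by √(1 + 0.2²/2.28) = 1.009 to √(1 + 0.5²/2.28) = 1.053, about 1% to 5%. The clustering fix does not depend on this.
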